- A significance level of $\alpha = 0.05$ (two-tailed).
- A desired power of 0.9

Based on these assumptions, a sample size of 26 subjects is required to achieve a power of 90%.

A sample size of 100 adult subjects will be enrolled in the clinical investigation, this large sample will allow for additional analyses to be conducted specifically the additional patient reported outcome measures, where a large sample size is typically desired. Additionally the sample size provides greater justification for generalizability to the wider clinical population.

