4.5.2 Subgroup Analyses

The consistency of the primary endpoint will be examined across subgroups of subjects defined by the following baseline characteristics: age, gender, and duration of hearing loss, baseline CNC word scores, and existing medical comorbidities. Any significant difference between subgroups on endpoints will be explored with additional analyses. Additionally, for the analysis of age subjects will be stratified into 2 groups according to age at time of surgery: 1). <65 years and 2). ≥ 65 years. The effect of age may further be investigated by examining outcomes by decade.

Additional analyses will be completed to evaluate speech perception in quiet and noise at 6 months in the best bilateral listening condition – for most subjects this will be the bimodal condition (CI + contralateral hearing aid), and for others this will be the combined condition CI + Acoustic hearing (same ear) + contralateral hearing aid). Additionally, a subgroup analysis will be done for: Subjects using bimodal hearing and subjects using combined hearing. Differences between and within the subgroup will be evaluated.

Subgroup analysis will be done for: Subjects using hybrid hearing (acoustic + electric in the implanted and subjects using electric alone. Differences between and within the subgroup will be evaluated for primary and secondary endpoints.

The number of subjects falling into each group following surgery cannot be predicted consequently, sample size is not adjusted based on these subgroup analyses.

In addition, the consistency of the primary endpoint will be examined across investigational sites by testing for an effect of site in ANOVA model. Any potential variation between sites in the primary endpoint will be explored by assessing whether or not there are differences in baseline characteristics between subjects at sites that might explain the results.

Exploratory analyses may be conducted to determine factors that predict performance on a CNC word score at 6 months.

Factors that will be considered are:

- Demographic variables such as age, degree of hearing loss, duration of hearing loss
- Other preimplant variables such as: CNC word score, AzBio +10 score, AzBio +5 score, PTA, LFPTA, SSQ score, HUI score and MoCA score (pass/fail)
- Surgical factors, such as surgical approach, speed of insertion of sheath and electrode and number of white markers visible

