The Mini TQ is a 12-item questionnaire that defines a general dimension of distress as a result of tinnitus. The Mini TQ will be recorded for each subject at baseline, at six month and 12 months follow-up. The differences between each follow-up Mini TQ and baseline Mini TQ will be analyzed by reporting the proportion of subjects who reported for each of the statements “TRUE”, PARTLY TRUE”, NOT TRUE. Additionally, the differences between each follow-up Mini TQ and baseline Mini TQ (i.e. change in baseline) may be analyzed using a repeated measure, mixed effects model, with the Mini TQ difference as the response and variables such as speech perception, age and gender as the explanatory variables.

Patient Based Resource and Expenditure Questionnaire (PBRE)

The PBRE questionnaire (assessed at baseline, and 6 Months) will be used to collect self-reported costs of hearing loss pre- and post-cochlear implantation. The differences between the 6 month follow-up PBRE and baseline PBRE (i.e. change in baseline) will be analyzed by reporting the proportion of subjects responding on selected questions.

Montreal Cognitive Assessment -MoCA

The MoCA is a rapid screening instrument for mild cognitive dysfunction. It assesses different cognitive domains: attention and concentration, executive functions, memory, language, visuoconstructional skills, conceptual thinking, calculations, and orientation. The baseline and six month follow-up MoCA score will be recorded for each subject. The proportion of subjects who pass (i.e. score 26 or higher) and those who fail a score of below 26 will be reported. Subjects who demonstrate ≥ 2 or ≤ 2 change in their score from baseline to 6-month will be reported as significant if it moves them into or out of a category (i.e. pass versus fail) (Personal communication [name].)

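### MoCA is listed as pass/fail in the optional analysis of predictors of 6-month CNC although its numeric baseline score is recorded; if the relation is roughly linear, this loses information.

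*SAP*

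**What the plan says.** SAP section 4.5.2 (Subgroup Analyses) states: "Exploratory analyses may be conducted to determine factors that predict performance on a CNC word score at 6 months". It then groups the factors to be considered: demographic, other preimplant, surgical, electrode and post-implant. The preimplant group names CNC, AzBio at two signal-to-noise ratios, two pure tone averages and SSQ, and ends with "HUI score and MoCA score (pass/fail". None of the others is given in categories.

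SAP section 4.5.5 (Patient Reported Outcomes) describes the instrument and states: "The baseline and six month follow-up MoCA score will be recorded for each subject". It defines the categories: "The proportion of subjects who pass (i.e. score 26 or higher) and those who fail a score of below 26 will be reported". It also uses the size of a change, beginning "Subjects who demonstrate ≥ 2 or ≤ 2 change in their score from baseline to 6-month", and counts such a change as significant only if the subject also moves between pass and fail.

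**The concern.** A threshold of 26 serves a screening purpose, and reporting the proportions who pass and fail is a sensible description of the cohort. Finding factors that predict a continuous outcome is a different task. There, the binary form treats a score of 25 like a score of 15, and treats 25 and 26 as opposites. The numeric score is already collected, and the SAP does not say why it is set aside.

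What is at stake is the chance of seeing a cognitive effect on 6-month CNC if there is one. MoCA is the only cognitive measure in the list, so a null finding for cognition could reflect the coding rather than the absence of a relation.

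**Working it through.** **The plan's own figure.** The SAP gives no sample size, power or effect for the predictor analysis, so there is nothing on this point to reproduce.

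**Inputs from the SAP**
- MoCA as a predictor: pass/fail (4.5.2), with pass at 26 or higher (4.5.5).
- Numeric score: recorded at baseline and 6 months (4.5.5).
- Number of subjects: "A sample size of 100 adult subjects will be enrolled in the clinical investigation" (4.1). This is an upper bound, because section 7.0 leaves subjects withdrawn before 6 months out of the final cohort.

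**Inputs assumed, because the SAP does not give them**
- A roughly linear relation between MoCA and 6-month CNC, and a near-normal MoCA score.
- A pass share p, shown over a range.
- For the power illustration only, a true correlation of 0.30.

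**Step 1: information kept.** When a normal, linearly related predictor is cut so that a share p falls on one side, the share of information kept is the squared correlation between the binary and the numeric form: φ(z_p)² / [p(1 − p)]. Here z_p is the normal quantile at p and φ is the normal density.

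- At 50/50: 0.399² / 0.25 = 0.637
- At 30/70: 0.348² / 0.21 = 0.576
- At 20/80: 0.280² / 0.16 = 0.490
- At 10/90: 0.1755² / 0.09 = 0.342

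| Pass/fail split | Kept | Lost | 100 subjects count as |
|---|---|---|---|
| 50/50 | 64% | 36% | 64 |
| 30/70 | 58% | 42% | 58 |
| 20/80 | 49% | 51% | 49 |
| 10/90 | 34% | 66% | 34 |

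The formula is symmetric, so it does not matter which side is the smaller. The loss reaches 50% at a share of about 21%.

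**Step 2: check on a discrete score.** The calculation was repeated for a whole-number score from 0 to 30 cut at 26, with assumed means of 22 to 27 and SDs of 2.5 to 3.5. The loss was 32% to 44% for pass shares of 27% to 70%, about 49% to 52% for shares of 20% to 23%, and 56% to 70% for shares of 8% to 16%. The normal approximation is therefore adequate.

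**Step 3: what this does to power.** With n = 100, two-sided alpha 0.05 and the Fisher z approximation, power ≈ Φ(atanh(r)·√97 − 1.96).
- Numeric score, r = 0.30: 0.3095 × 9.849 − 1.96 = 1.09, so power is about 86%.
- Pass/fail: r shrinks by the square root of the share kept. At 50/50, r = 0.30 × 0.798 = 0.239 and power is about 67%. At 30/70 it is about 63%, at 20/80 about 56%, and at 10/90 about 42%.

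**Step 4: the limiting case.** If the true effect is a step at exactly 26, the binary form is the correct model and loses nothing.

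**The case against.** The case for leaving the text alone has several parts.

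- **The analysis is optional and the list is open.** Section 4.5.2 says the analyses may be done and introduces the variables by way of example. A reader might infer that the numeric score is ruled out. The text does not say that; it only names the binary form. This stands and limits the weight of the point.
- **The cut is prespecified and matches the plan's own use of MoCA.** It is not data-driven, and 4.5.5 reports MoCA by pass and fail. That supports pass/fail for description. It is not a reason to use it for prediction, and 4.5.5 itself also looks at the size of a change.
- **The size of the loss is conditional.** A reader might infer that the plan certainly throws away a third to a half of the information. The SAP gives neither the distribution nor the shape of the relation, so that cannot be stated as fact.
- **No ranking of predictors is planned.** A reader might infer that MoCA will be unfairly ranked against predictors kept on their full scale. The SAP specifies no model, selection rule or comparison of importance, so this is not supported. Nor is MoCA rare in not being a hearing test: age, questionnaire, surgical and electrode factors are listed too. What holds is that it is the only cognitive measure.
- **The change is not entirely free.** A linear term relies on linearity. A spline spends degrees of freedom in an analysis with many candidate factors and at most 100 subjects. This stands, and is why a linear term is the simpler default.

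What remains is that a recorded numeric score is named in a less informative form, with no reason given.

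**Conclusion.** The point holds as a minor improvement to an optional exploratory analysis. Under a roughly linear relation, a near-normal score and a pass share of about 20% to 80%, the cut discards about 36% to 51% of the information that MoCA carries about 6-month CNC. For this predictor, that is like analysing 49 to 64 subjects instead of 100. None of the three assumptions comes from the SAP. A more uneven split raises the loss (66% at 10/90), and a true step at 26 brings it to nil.

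A reader might infer that the efficacy conclusions are affected. They are not: the predictor analysis lies outside the fixed-sequence tests of section 4.4, so no primary or secondary conclusion changes.

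**What to change.** In the preimplant list of section 4.5.2, replace the pass/fail form of MoCA with the numeric baseline score, entered as a linear term. Keep pass/fail at 26 for the descriptive reporting in 4.5.5 and, if wanted, as a sensitivity analysis, which would also cover the possibility of a threshold effect.

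The cost is one phrase in the SAP, with no new data. The small downside is the linearity assumption, or the extra degrees of freedom if a spline is preferred.

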- Electrode factors such as, electrode location, WF, basal angle of insertion and apical angle of insertion
- Post implant variables: hours of device use, CNC word score at 3 months, AzBio +10 at 3 months, HUI and SSQ scores at 6 months

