4.5.4 Imaging

Post-operative CT Scans will be analyzed through 3D reconstruction to report on:

- Placement of the electrode in the cochlea: Scala Tympani versus Scala Vestibuli
- Measurement of modiolar proximity also known as the wrapping factor, scores will range between 0 -1, with 0 being the closest to the modiolus and 1 being furthest on the lateral wall. Wrapping factor will be reported as a percentage.

Possible exploratory analysis may be completed to determine if there is a correlation between the electrode placement and wrapping factor any surgical technique factors as reported on the surgical questionnaire with speech perception (CNC word score and AzBio Sentences in noise).

Electrode position will be also correlated with T& C levels and impedance values after at least 60 days of device use.

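### The list of factors said to predict 6-month CNC includes HUI and SSQ taken at the same 6-month point, and mixes 3-month scores with earlier factors without staging

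*SAP*

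**What the plan says.** SAP section 4.5.2 states the aim: "Exploratory analyses may be conducted to determine factors that predict performance on a CNC word score at 6 months". A single list follows, introduced by "Factors that will be considered are". It has five bullets: demographic, preimplant, surgical, electrode and post-implant. The last reads: "Post implant variables: hours of device use, CNC word score at 3 months, AzBio +10 at 3 months, HUI and SSQ scores at 6 months". The items chiefly at issue are the final ones, "HUI and SSQ scores at 6 months".

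The section gives no model form, order of entry, staging or selection rule, and does not say whether factors are examined singly or together.

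Four other places bear on the point:

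- Section 4.3.2 makes HUI3 at 6 months a secondary endpoint.
- Section 4.5.5 tests the change in SSQ from baseline to 6 months. It also allows an optional mixed model in which the SSQ change is the response and speech perception is an explanatory variable.
- Section 4.5.4 offers a separate optional analysis: "Possible exploratory analysis may be completed to determine if there is a correlation between the electrode placement and wrapping factor", and surgical technique factors, on one side and CNC and AzBio scores on the other. It names no post-implant covariates.
- Section 8.0 commits the sponsor to publishing the results of the SAP's analyses in full.

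**The concern.** There are two problems of different strength.

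The first does not depend on the model. A predictor has to be known before the outcome. HUI and SSQ at 6 months are not; they are self-reported results at the time point at which CNC is scored. Even if each factor were tested alone, a correlation between 6-month SSQ and 6-month CNC would be reported under the label of prediction. Section 4.5.5 treats the relation the other way round, with speech perception explaining SSQ, so the SAP is not consistent about which is the response.

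The second depends on the model. CNC and AzBio at 3 months are early readings of the same performance and lie downstream of the preoperative, surgical and electrode factors. If they enter one regression with those factors, the coefficient of an earlier factor no longer measures its whole relation to 6-month CNC, only what is left after early performance is held fixed. A factor that acts through early performance could then look unimportant. Because section 8.0 promises publication, such a result, if the analysis is run, would be read outside the study team.

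**Working it through.** **The plan's own figures.** The SAP gives no figure for this analysis. Its sample size for the CNC endpoint (difference 15, SD 22.4, two-tailed alpha 0.05, power 0.90) reproduces at 26 with the noncentral t distribution, but does not bear on the point.

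**Timing of the listed factors against the outcome (CNC at 6 months).**

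- Before activation: demographic, preimplant, surgical and electrode factors. These can predict.
- At 3 months: CNC and AzBio +10. These can predict from 3 months on, but are also consequences of the group above.
- After activation, period not stated in the SAP: hours of device use.
- At 6 months: HUI and SSQ. These are concurrent and cannot predict.

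**Size of possible masking under joint entry.** All correlations here are assumptions. Only n = 100 comes from the SAP (section 4.1), and it is the planned enrolment. Variables are standardised. One true baseline factor x has correlation r = 0.30 with CNC at both 3 and 6 months. The two CNC scores correlate at c and share one underlying ability. One 6-month questionnaire score depends on 6-month CNC with correlation h.

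The coefficient of x on 6-month CNC is:

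- x alone: r = 0.30.
- with the 6-month questionnaire score: r(1 − h²)/(1 − h²r²). For h = 0.4: 0.30 × 0.84/(1 − 0.0144) = 0.252/0.9856 = 0.26.
- with 3-month CNC: r(1 − c)/(1 − r²). For c = 0.7: 0.30 × 0.30/0.91 = 0.099, about 0.10.

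The chance of detecting x (two-sided 0.05) was simulated with ordinary least squares, 2,000 runs per setting:

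| Entered beside x | Assumed correlation with 6-month CNC | Coefficient of x | Detection |
|---|---|---|---|
| nothing | – | 0.30 | about 86–87% |
| 6-month questionnaire score | h = 0.2 | 0.29 | about 85% |
| | h = 0.4 | 0.26 | about 80% |
| | h = 0.6 | 0.20 | about 68–71% |
| 3-month CNC | c = 0.6 | 0.13 | about 33% |
| | c = 0.7 | 0.10 | about 25% |
| | c = 0.8 | 0.07 | about 18% |
| | c = 0.9 | 0.03 | about 11% |
| both | all combinations | 0.03–0.13 | about 11–32% |

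**A second set of assumptions.** Here a preoperative factor correlates 0.4 with true performance; reliability is 0.85 for 6-month and 0.70 for 3-month CNC; true performance correlates 0.5 with 6-month SSQ and 0.35 with 6-month HUI. Detection is 97% with the factor alone, 87% with 6-month SSQ and HUI added, about 47% with 3-month CNC added instead, and about 40% with all three.

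In both sets most of the loss comes from the 3-month score. If factors are examined singly, or earlier factors are modelled without post-implant variables, there is no loss.

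**The case against.** A reader might infer that real preoperative, surgical and electrode predictors will be masked. The SAP does not support that. The analysis is optional, the factors are only to be considered, and no joint model is stated. The bullets are grouped by stage, so single-factor or staged analyses fit the text equally well. Several factors also have another route to CNC without adjustment for later scores. Section 4.5.2 examines the primary endpoint across age, gender, duration of hearing loss, baseline CNC and comorbidities, and section 4.5.4 permits correlations for electrode and surgical factors. All of this stands, so masking is a possibility under one modelling choice.

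It is also fair that the 3-month scores, which drive most of the masking, are legitimate if the aim is prognosis from 3 months on. That argues for a separate model, not for dropping them.

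A second tempting inference is overfitting. The list names 3 + 8 + 3 + 4 + 5 = 23 factors. With 23 pure-noise predictors and 100 subjects the expected R-squared is 23/99 = 0.23, and 23 independent tests give a chance of 1 − 0.95^23 = 0.69 of at least one p < 0.05. The first figure assumes one model holding all 23 factors, which the SAP does not plan; nor does it promise an R-squared. The second is ordinary multiplicity in any exploratory screen, which the exploratory label already concedes. Neither arises from HUI or SSQ, and neither is part of this point.

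None of this rescues 6-month HUI and SSQ as predictors. If prediction was meant loosely as association, the wording should say so.

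**Conclusion.** The point holds in two parts. Listing 6-month HUI and SSQ as predictors of 6-month CNC is wrong as written, under any model; this rests on the SAP text alone. The undivided list also leaves room for a joint model in which true earlier effects could be masked, mainly by the 3-month scores. Under the first set of assumptions, detection of a true baseline factor falls from about 87% to 11–33% with 3-month CNC, and to about 68–85% with a 6-month questionnaire score alone. Those sizes rest on assumed correlations and on all 100 subjects contributing data.

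The primary and secondary endpoints, their tests and the sample size are untouched. This is a minor correction.

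**What to change.** In section 4.5.2:

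1. Take 6-month HUI and SSQ off the predictor list and report them as concurrent associations with 6-month CNC.
2. Model the demographic and other preoperative, surgical and electrode factors first, without any post-implant variable.
3. Put the 3-month CNC and AzBio scores and device use in a separate model, labelled as an early-course model, and state the period over which device use is counted.

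The cost is a change of SAP wording and slightly more analysis, with no new data. Any R-squared that is reported will be lower, because the same-time outcomes no longer contribute to it.

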4.5.3 Change in Audiometric Thresholds

This is not a hearing preservation study and as such loss of low frequency hearing will not be tracked as an adverse event, changes in low frequency will be documented and reported. Specifically:

- The change in the low frequency pure tone average audiometric threshold in dB (125 Hz-750 Hz LFPTA) at each interval (IA, 1, 3, 6 and 12 months) will be calculated for each subject.
- The change in the audiometric threshold in dB at 500 Hz at each interval (IA, 1, 3, 6 and 12 months) will be calculated
- Additionally the effect of age on the change in LFPTA at each interval will be calculated. The effect of age will further be analyzed by stratifying the subjects into 2 groups based on their age at time of enrolment: <65 years of age and ≥65 years of age. Differences between and within the groups will be evaluated.

Additionally, the audiometric results will be reported according to the AAO Consensus on minimal reporting (Adunka, 2018)

These results will be documented in an Annual Progress Report and in publication(s).

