3.0 Subject Population

Study sites will enroll 100 adult cochlear implant candidates at up to 15 North American cochlear implant centers.

Cochlear Americas will adhere to the National Coverage Determination (NCD) for Cochlear Implantation for enrollment of Medicare beneficiaries into the Clinical Evaluation of the Cochlear Nucleus® CI532 Cochlear Implant in Adults. Specifically, the following NCD criteria will be met:

1. Diagnosis of bilateral moderate-to-profound sensorineural hearing impairment with limited benefit from appropriate hearing (or vibrotactile) aids, defined as test scores of less than or equal to 40% correct in the best-aided listening condition on tape-recorded tests of open-set sentence recognition;
2. Cognitive ability to use auditory clues and a willingness to undergo an extended program of rehabilitation;
3. Freedom from middle ear infection, an accessible cochlear lumen that is structurally suited to implantation, and freedom from lesions in the auditory nerve and acoustic areas of the central nervous system;
4. No contraindications to surgery.

Candidates must also meet the following inclusion and exclusion requirements as stated in the study protocol:

Inclusion Criteria:

1. Adults 18 years or older who have a bilateral postlinguistic sensorineural hearing loss.
2. Limited benefit from amplification as defined by test scores of 40% correct or less in the ear to be implanted and 50% or less in the contralateral ear on a recorded monosyllabic word test
 - I. Consistent with the Minimum Speech Test Battery (2011), it is required that all subjects be evaluated at 60 dBA presentation level.
3. Bilateral moderate sloping to profound hearing loss

4. Minimum of 30 days experience with appropriately fit bilateral amplification, fit using the standardized NAL fitting method
5. Proficient in English
6. Ability to complete testing

Exclusion Criteria:

1. Previous cochlear implantation
2. Pre-linguistically deafened (onset of hearing loss at less than two years of age)
3. Ossification or any other cochlear anomaly that might prevent complete insertion of the electrode array
4. Duration of severe to profound hearing loss greater than 20 years
5. Diagnosis of retro-cochlear pathology
6. Diagnosis of auditory neuropathy
7. Unrealistic expectations on the part of the subject regarding the possible benefits, risks, and limitations that are inherent to the surgical procedure and use of the prosthetic device

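### Section 4.5.3 compares LFPTA change between age groups without preoperative LFPTA, so the audiometer limit can dilute the summarised loss and can create a false age difference

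*SAP*

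**What the plan says.** SAP section 4.5.3 sets out three analyses of threshold change.

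- LFPTA change: "The change in the low frequency pure tone average audiometric threshold in dB (125 Hz-750 Hz LFPTA) at each interval". This change "at each interval (IA, 1, 3, 6 and 12 months) will be calculated for each subject".
- A single-frequency measure: "The change in the audiometric threshold in dB at 500 Hz at each interval", over the same intervals.
- An age analysis: "the effect of age on the change in LFPTA at each interval will be calculated", followed by a split at enrolment into "<65 years of age and ≥65 years of age". Of this split the section says: "Differences between and within the groups will be evaluated".

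The section names no subset of ears with measurable preoperative low-frequency hearing, no value for a no-response threshold, no model for the age analysis and no adjustment for preoperative LFPTA. It states that the study is not about hearing preservation and that low-frequency loss is not tracked as an adverse event. It adds that audiometric results will follow an external consensus on minimal reporting.

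On entry, section 3.0 requires under the coverage criteria "Diagnosis of bilateral moderate-to-profound sensorineural hearing impairment". Inclusion criterion 3 runs from moderate sloping to profound loss. Neither sets a limit on low-frequency thresholds, and severe to profound loss is excluded only when it has lasted more than 20 years. Section 4.5.2 lists LFPTA among the preimplant variables, but only as a possible predictor of the 6-month CNC word score.

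**The concern.** Threshold change has an upper bound: the audiometer limit minus the preoperative threshold. An ear with no response before surgery is recorded with a change of about 0 dB, which looks the same as an ear whose hearing was preserved. Any group summary of change mixes the two.

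The same bound affects the age contrast. If one age group starts with poorer low-frequency thresholds, its ears have less room to change. Its raw change is then smaller even when the underlying loss is identical, and the comparison would show an age effect that is partly a difference in preoperative hearing.

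Because low-frequency loss is kept out of adverse event tracking, section 4.5.3 is the only account of it that the SAP defines. Its results go to the Annual Progress Report and to publications.

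**Working it through.** The SAP states no expected loss, SD, measurable share, audiometer limit or power for this analysis, so there is no figure of its own to reproduce. All numeric inputs below are assumptions; only the structure (change per subject, two age groups, no covariate) comes from section 4.5.3.

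**Step 1, simple dilution.** Let q be the share of ears with no preoperative response (change recorded as 0) and m the mean loss in the others. The all-ear mean is m × (1 − q).

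| m | q = 10% | q = 20% | q = 30% | q = 50% |
|---|---|---|---|---|
| 20 dB | 18 | 16 | 14 | 10 |
| 30 dB | 27 | 24 | 21 | 15 |

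**Step 2, simulated dilution.** Preoperative LFPTA is normal with SD 20 dB. The underlying shift is normal with mean 25 and SD 12 dB. A single limit L applies to both readings:

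change = min(pre + shift, L) − min(pre, L)

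| L | Preoperative mean | No response before surgery | All ears | Measurable ears | Gap |
|---|---|---|---|---|---|
| 120 | 60 | 0% | 24.3 | 24.4 | 0.1 |
| 110 | 60 | 1% | 23.4 | 23.5 | 0.1 |
| 110 | 90 | 16% | 14.7 | 17.4 | 2.7 |
| 100 | 90 | 31% | 10.3 | 14.9 | 4.6 |

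Over L = 100 to 120 dB and preoperative means of 60 to 90 dB, the gap runs from about 0.1 to 4.6 dB.

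**Step 3, age contrast with identical underlying shift.** L = 110 dB, younger-group preoperative mean 75 dB.

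| Baseline LFPTA difference | False difference, all ears | Measurable ears only | All ears, preoperative LFPTA as linear covariate |
|---|---|---|---|
| 0 dB | 0.0 | 0.0 | 0.0 |
| 5 dB | 1.6 | 1.1 | 0.1 |
| 10 dB | 3.4 to 3.5 | 2.3 | 0.15 |
| 15 dB | 5.5 | 3.6 | 0.3 |

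**Step 4, other inputs.**

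- L = 105 dB, preoperative means 60 versus 70 dB, SD 20 to 22 dB, shift normal(25, 15) with negative values set to 0: all-ear mean change is 19.4 to 22.4 dB. The false age difference is about 2.5 dB, falling to 0.02 to 0.06 dB with the covariate.
- Grid of step 2, every pair of preoperative means 10 dB apart: the false difference runs from about 1.0 dB (L = 120; 60 versus 70) to 4.3 dB (L = 100; 80 versus 90). The covariate leaves at most about 0.26 dB.

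The covariate therefore removes nearly all of the false age difference in these settings. Restriction to measurable ears alone leaves most of it: 2.3 of 3.4 dB at a 10 dB baseline difference.

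**The case against.** Several points on the other side are sound.

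- A reader might infer that the plan averages change over every subject and so understates the loss. The text says only that change is calculated for each subject. It names no mean, and a value per subject is compatible with later stratification. Only the age comparison implies a group summary. An all-ear mean also describes the measured change in the enrolled cohort correctly; it is low only relative to ears that had hearing to lose.
- A reader might infer that the age comparison does reflect preoperative hearing. That requires the age groups to differ in preoperative LFPTA, and the SAP gives no baseline LFPTA by age. With equal baselines the false difference is zero.
- Inclusion criterion 3 speaks of sloping loss, which can be read as an audiogram with better low-frequency hearing. LFPTA covers only 125 to 750 Hz, so few ears may be near the limit.
- The external reporting consensus may cover no-response handling. Its content is not in the document, so it can neither be credited nor assumed silent. As cited, it is an addition to the three analyses and does not define their subjects or covariates.
- The effect may be small against sampling error. With 50 subjects per age group (an assumed split) and a simulated SD of change of 13 dB, the standard error of the difference is √(2 × 13²/50) = 2.6 dB, about the size of the 2.5 dB false difference.

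These points limit the certainty and size of the bias. They do not show that the age comparison is protected against it: the section plans that comparison and names no baseline term, although preoperative LFPTA is listed for another analysis.

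**Conclusion.** The point holds in conditional form. As written, the age analysis in section 4.5.3 can be confounded by preoperative low-frequency hearing through the audiometer limit, and any group summary of loss can be diluted by ears with little to lose.

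On assumed inputs, dilution is about 0.1 to 4.6 dB. The false age difference is about 2.5 to 4 dB for a 10 dB baseline difference in the central settings, with a range of about 1 to 4.3 dB over the full grid, and none at equal baselines. These sizes rest on an assumed limit, shift and baseline distribution, a single limit for the averaged threshold, and no measurement error in the preoperative value. The share of ears near the limit and the age-group baselines are not in the SAP, so the actual size is unknown.

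The analysis is descriptive and outside the fixed testing sequence of section 4.4. The primary and secondary conclusions are untouched.

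**What to change.** In section 4.5.3:

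1. Include preoperative LFPTA in the implanted ear as a covariate in the age analysis of LFPTA change, and show the unadjusted result beside it.
2. Summarise LFPTA and 500 Hz change separately for ears with and without measurable preoperative low-frequency thresholds. The sponsor should fix the cut-off, and the value recorded for no response, before the analysis; the SAP offers no basis for a particular number.
3. Report the proportion of ears with no response before surgery and at each interval after it.

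The cost is a few lines of SAP text and one added table. No new data are needed, since preoperative LFPTA is already collected. The drawback is smaller groups in the split summary.
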